- 2) Intervention group: Lean cohort: BMI ≤25, at <20 weeks gestation or BMI ≤28 at a term gestation, high dose oxytocin protocol
- 3) Control group: Obese cohort: BMI ≥30, at <20 weeks gestation or BMI ≥35 at a term gestation, low dose oxytocin protocol
- 4) Intervention group: Obese cohort: BMI ≥30, at <20 weeks gestation or BMI ≥35 at a term gestation, high dose oxytocin protocol

Primary outcome: Length of time to delivery (number of minutes from induction of labor to delivery). In case of cesarean delivery, length of time to delivery will be calculated from start time of induction to time when decision was made to proceed with cesarean delivery.

Secondary outcomes:

Length of time in 1st stage and 2nd stage of labor

Total amount of oxytocin, median, mean, and maximum oxytocin rate

Terbutaline use

Rate of cesarean delivery, and rate of cesarean delivery for labor arrest

Maternal and neonatal complications including, postpartum hemorrhage, uterine rupture, tachysystole, chorioamnionitis, abnormal fetal heart tracing, fetal Apgar, neonatal intensive care unit admission rate, cord gas

3) Lay Summary (approximately 400 words)

Obesity is considered one of the biggest public health concern of the 21st century and increases the risk of many comorbid medical conditions. Obesity in pregnancy places women at higher risk of

				-		-	-	-	-	-	-	-	-	-	-	-	-
HSPP	Use	Onl	y:														
Form	200	v 2	016	5-0	7												

obstetrical complications during pregnancy, delivery and postpartum. In particular, obese pregnant women have more difficulty going into labor, a longer labor course, and even with pharmacologic treatment, have a higher chance of requiring cesarean delivery.

When pregnant women need help going into labor, they commonly receive a medication called Pitocin on the labor and delivery floor. Pitocin is the brand name and is a synthetic analog to the naturally produced oxytocin, a hormone secreted by mother when they naturally go into labor. This medication has been used widely around the world. There is emerging evidence that obese women need more oxytocin to go into labor compared to their lean cohorts. There are many studies to support the use of different oxytocin dosages and are currently supported by the American College of Obstetricians and Gynecologists. Despite these evidences, a low dose oxytocin regimen is universally used in the United States, regardless of patient characteristics.

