This study is a double blinded randomized controlled trial. Both lean and obese cohorts will be recruited for the study. We will randomly place both cohorts into the low or the high dose oxytocin regimen treatment group. The investigators, patients and providers will be blinded and will not know the specific assignments. The purpose of this study is to evaluate the effect of high dose oxytocin in the obese cohort. The hypothesis is that obese patient will have shorter time to delivery with the high dose oxytocin regimen without incurring any additional risks or adverse outcomes.

4) Setting of the Human Research

Recruitment and conduct of research for eligible patients will take place at the 8OPC/outpatient OB GYN clinic and the inpatient Labor and Delivery unit at the Banner University Medical Center.

5) Resources available to conduct the Human Research

The facility and resources at the outpatient 8OPC/OB GYN clinic and the inpatient labor and delivery unit at the Banner University Medical Center will be utilized to carry out this research study. This include 14 clinical rooms in the outpatient setting; 12 labor beds, 8 triage beds, and more than 20 postpartum beds in the inpatient setting. Both sites are staffed by 16 resident physicians, 3 maternal fetal medicine fellows, as well as attending physicians affiliated with the University of Arizona at their regular business hours. Additionally, both sites are fully supported by nursing and other clinical staffs. There are always 24 hours nursing and in house physician care in the inpatient setting.

The department of statistics will be asked to provide a randomization sequence for the lean patients and a separate sequence for the obese patient to be enrolled in the trial. The lists will be provided to the research pharmacy. The research pharmacy will be responsible for creating the different concentrations of oxytocin infusion drugs which will be labeled as "OPS drug" (Obese Pitocin Study). They will also be responsible for the allocation concealment and blinding aspect of the randomized controlled trial. Bags of oxytocin infusion will appear identical but will contain either low dose or high dose concentrations. The bags will be labelled with study number only (the pharmacist preparing the bags will be the only person able to access the information on study allocation via their list).

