Subsequently after delivery, a new bag of usual concentration of oxytocin will be used in all 4 groups for postpartum oxytocin as per routine.

When the maximum rate is reached at 20cc/hour, patient will be assessed by the provider for eligibility to continue to increase oxytocin dosage. This will also be done in the routine manner at the discretion of the provider.

All woman/fetus pairs will be continuously monitored via Doppler/TOCO as per standard of care.

Subject participation is expected to last until time of hospital discharge.

Data collection

Standard data points will be collected during the labor of each patient enrolled in the study:

Demographic:

Date of admission and discharge

Age, race, parity, gravidity

Weight, height and BMI

Indication for induction

Associating medical comorbidities

Induction:

Cervical exam and bishop score

Start time for induction

Tachysystole

Terbutaline use

Internal monitoring (intrauterine pressure catheter, fetal scalp electrode)

Time of membrane rupture (spontaneous or artificial)

Time of onset of second stage labor

Time of delivery of fetus, placenta

Birth weight of fetus

Apgar score of fetus at 1 and 5 minutes

Type of delivery (vaginal, vacuum or forceps assisted, cesarean delivery) and indication

If cesarean delivery, time when decision of cesarean delivery was made

Total amount of oxytocin, median, mean, and maximum oxytocin rate

Abnormal fetal heart tracing

Maternal complications

Postpartum hemorrhage

Estimated blood loss

Postpartum fever, chorioamnionitis, endomyometritis

Pre-induction and Lowest postpartum hematocrit

Uterine rupture

Blood transfusion

Incidence of oliguria

Baby:

Type of nursery admission (newborn or NICU)

Umbilical cord gas if applicable

No other PHI will be collected as part of this study.

All the data above will be collected from the medical records and transcribed on a standardized data collection sheet and will be placed in a locked cabinet in the investigator's office (please see attachment for data collection sheet).

9) Cost to subjects

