These are well known side effects of oxytocin on the obstetrical floor and the absolute rates remain low. Again, as discussed above, these risks were evaluated and compared directly by multiple meta-analysis and a Cochrane review. There was also no difference in serious maternal or neonatal morbidity or death between the high and low dose regimen. There was no difference in adverse outcomes, including maternal uterine rupture, postpartum hemorrhage, endometritis, estimated blood loss, abnormal fetal heart tracing, fetal Apgar, newborn resuscitation and neonatal intensive care unit admission ³⁻⁵. Therefore, the investigator believes that the risk to the patient will be similar to baseline.

Tachysystole will be monitored continuously as a clinical parameter to direct patient care and protocol management as well as a secondary outcome variable.

Endocrine and metabolic: Water intoxication (SAE), hyponatremia (SAE)

Again, as described above, there were also old case reports originating from the 1970s about concerns over high dose oxytocin and its association with maternal hyponatremia or water intoxication ^{6,7}. The hypothesis behind its association is due to the similarity between oxytocin and anti-diuretic hormone. These were largely single case reports in the setting of accidental large overdose of oxytocin in addition to large volume administration of electrolyte-free solutions. Since then, the practice of administering oxytocin is only given alongside isotonic lactated ringer or normal saline in a slow intravenous infusion fashion ^{8,9}. This study does not deviate from the standard of care. Therefore, the investigator predicts a low risk to patients, risks that would be comparable with current standard of care.

The following SAE and AE have been associated with oxytocin but frequency is not well defined and not well reported in the literature.

Hematologic: pelvic hematoma (SAE), fatal afibrinogenemia (SAE)

Misc: Anaphylactic reaction (SAE), nausea and vomiting (AE)

Risks to fetus include:

Due to induced uterine motility: bradycardia (SAE), premature ventricular contractions and other arrhythmias (SAE), permanent CNS or brain damage (SAE), fetal death (SAE), neonatal seizures (SAE)

Due to use of oxytocin in mother: low apgar scores (AE), neonatal jaundice (AE), neonatal retinal hemorrhage (SAE)

Frequency of risks:

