The frequency of risks occurring for each risk is not well defined and not well reported in the literature. All above risks are considered to be rare, with the exception of:

Tachysystole: This will be monitored continuously as a clinical parameter to direct patient care and protocol management, as written in the protocol. Also it is important to recognize that tachysystole occurs with the low dose protocol as well, which is the current standard of care.

Nausea and vomiting: This is a common side effect of labor itself with or without oxytocin.

It is important to recognize that these risks exist equally in the low dose protocol, which is the current standard of care on Labor and Delivery. When a patient presents for an induction of labor with oxytocin, they are subjected to all of the above risks, regardless of whether they are enrolled as a study participant. The only way to avoid these risks completely, is for a patient to not receive oxytocin (which is required if patient agreed to undergo an induction of labor). These risks above have been well monitored throughout clinical practice since the 1970s, and large Cochrane review as detailed above had provided good safety profile for this drug in both the low and high dose regimen.

All serious adverse events (SAE) will be monitored and documented closely during the study, and will result in discontinuation of the study protocol immediately. The management of AE is detailed in the protocol. If more than 20% of patients enrolled in the study have an AE/SAE, enrollment in the study will be stopped pending an evaluation of the frequency of AE/SAE.

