For every 10 enrollments, data will be monitored by the principal investigator and reviewed by an independent reviewer within the department of ob/gyn. This personnel will have a background in ob/gyn and will be assigned by the principal investigator. Data will be reviewed in a blinded fashion to prevent introducing bias into the study. In addition, all serious adverse events (SAE) will be monitored and documented closely during the study with each enrollment, and will result in discontinuation of the study protocol immediately. The management of AE is detailed in the protocol. If more than 20% of patient enrolled in the study have an AE/SAE, enrollment in the study will be stopped pending an evaluation of the frequency of AE/SAE. This will be reported to the IRB. The principal investigator and the research staffs will monitor protocol adherence closely with each enrolled participant. Any protocol deviation will be reported to the IRB as required.

17) Withdrawal of subjects

A patient may withdraw from this research at any time. The infusion of the study drug can be stopped at any time. A patient may withdraw for any reason, including a desire to stop induction of labor and undergo an elective cesarean delivery. Subjects will not be at increased risk when they are abruptly withdrawn from the study because of the short half-life of oxytocin (4.5 minutes). Data collection on patients who have completed more than 30 minutes of study drug will be kept and included in the data analysis (intention to treat analysis). Any withdrawal secondary to side effects or adverse effects will be recorded and monitored. Only verbal withdrawal is required.

18) Sharing of results with subjects

The results of the study will not be shared with the subjects, families or the institution. Patients will not be contacted in the future in relation to the results of the research. The intention is to publish the results of this research and patients will have access to the information gained through this forum.

There will be no additional charges billed to the insurance for any procedures associated with this study.

19) Future use and long-term storage of data or specimens

Data will not be kept for future research.

20) Clinical Trials.gov Information

	ClinicalTrials.gov "NCT" number for this trial (provide):
\boxtimes	Registration pending
	Clinical trial does not require registration (explain):

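### The 20% AE/SAE enrollment pause pools both doses and, as worded, counts nausea and vomiting, so it cannot separate a high-dose excess from shared background

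*Combined protocol and SAP*

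**What the plan says.** The rule stands in section 10 (Risks to subjects) and is repeated almost word for word in section 16 (Monitoring for subject safety): "If more than 20% of patients enrolled in the study have an AE/SAE, enrollment in the study will be stopped pending an evaluation" of how often AEs and SAEs occur. The denominator is everyone enrolled, low and high dose together. No derivation of the 20% is given, and section 10 says that event frequencies are not well defined.

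Section 10 lists nausea and vomiting as an AE, then says of it: "Nausea and vomiting: This is a common side effect of labor itself with or without oxytocin". As worded, it counts toward the 20%. Section 8 introduces its data collection list with "Standard data points will be collected during the labor of each patient enrolled in the study". That list includes tachysystole but not nausea or vomiting.

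On review, section 16 says: "For every 10 enrollments, data will be monitored by the principal investigator and reviewed by an independent reviewer within the department of ob/gyn", and "Data will be reviewed in a blinded fashion to prevent introducing bias into the study". On access to allocation, section 5 says that "the pharmacist preparing the bags will be the only person able to access the information on study allocation via their list".

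Other safeguards bear on this point. Sections 10 and 16 say that every SAE is monitored and leads to immediate discontinuation of the study protocol. Section 8 gives each arm a dose-reduction rule for tachysystole. Section 2 lists secondary outcomes for the four groups: "Maternal and neonatal complications including, postpartum hemorrhage, uterine rupture, tachysystole, chorioamnionitis" and others.

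**The concern.** The Lay Summary (section 3) hypothesizes a shorter labor on high dose with no added risk. The high-dose bag is three times the standard concentration. During enrollment, the safety question is whether a run of events belongs to that higher concentration. A share pooled over both doses answers a different question: whether events are frequent overall.

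Two outcomes would be unhelpful: a pause caused by a common event unrelated to dose, or silence while high dose carries a real excess. In neither case does the plan give the reviewer a table that would show which it is. At stake are unnecessary interruptions to enrollment and late recognition of a dose-related excess.

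**Working it through.** The threshold has no stated derivation, so there is no plan figure to reproduce.

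**Inputs from the protocol.** Threshold: more than 20% of enrolled women. Reviews: every 10 enrollments. Total 140, randomized 1:1 within the lean and obese groups, so 70 per dose and 14 reviews.

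**Assumptions.** All event rates. Five women per dose in each block of 10. The 20% rule checked at the 10-enrollment reviews (the protocol does not tie the two together).

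**Formula.** With X(k) women having an event by review k,

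X(k) = X(k−1) + Bin(5, p_low) + Bin(5, p_high); pause if X(k) / (10k) > 0.20.

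This means at least 3 of 10 at the first review and at least 29 of 140 at the last. The chance of ever pausing comes from an exact recursion that removes paused trials at each review. As a hand check, at 20% in both arms the first review pauses with probability P(Bin(10, 0.20) ≥ 3) = 0.322; over all 14 reviews this becomes 0.763.

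**Step 1: dose excess against shared background.**

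| Low vs high dose | Average rate | Ever pauses |
|---|---|---|
| 10% vs 30% | 20% | 76% |
| 20% vs 20% | 20% | 76% |
| 5% vs 20% | 12.5% | 19% |
| 12.5% vs 12.5% | 12.5% | 21% |

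Scenarios with the same average give nearly the same answer, whatever the split. With background fixed, the rule does respond to dose: from 5% in both arms to 5% vs 30%, pauses rise from 1% to 55%.

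**Step 2a: nausea and vomiting counted.** Take other events at 5% in both arms and nausea/vomiting (nv) as independent of them, so total = 1 − (1 − 0.05)(1 − nv).

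| nv | Total, both arms | Ever pauses, no dose effect |
|---|---|---|
| none | 5% | 1% |
| 10% | 14.5% | 33% |
| 20% | 24% | 95% |
| 30% | 33.5% | >99.9% |

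At nv = 20%, a real 5% vs 20% excess in other events gives totals of 24% vs 1 − 0.80 × 0.80 = 36%, and pauses in 99.9%. Set against 95% with no excess, a pause says almost nothing about dose.

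**Step 2b: nausea and vomiting not captured.** At 5% vs 20% the pause fires in 19%, so the excess is missed in 100 − 19 = 81% of trials.

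Steps 2a and 2b are alternatives. They rest on opposite readings of what is counted.

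**Step 3: what a formal flag would add.** Suppose the coded-arm counts, without nausea/vomiting, are also tested at each review by Fisher's exact test at one-sided 0.025 in either direction. At 5% vs 20%, pause or flag has fired in 47% of trials by n = 70, 78% by n = 130 and 81% by n = 140. The last review comes too late to affect enrollment, so 78% is the relevant ceiling. With no dose effect (equal rates of 5% to 30%), the flag alone fires in about 2% to 12% over the trial. For rare events little is gained: 1% vs 5% triggers pause or flag in 9%.

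**The case against.** The strongest reply is that the pause is judged for a job that it does not claim. It is a provisional stop, followed by an evaluation and a report to the IRB. SAEs are handled outside it, and the SAE list is broad: it includes postpartum hemorrhage, uterine hypertonia, hypotension and fetal bradycardia. Tachysystole is monitored continuously and managed by reducing the infusion. This stands, and it narrows the point to non-serious AEs and to patterns across SAEs that handling each case alone would not reveal. The protocol does not say whether discontinuation after an SAE applies to the woman or to the trial.

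A reader might infer that the rule suffers both failures at once, pausing falsely and missing an excess. The documents do not support that: if nausea/vomiting is counted and common, background is not low. A reader might also infer that the rule ignores dose, that evaluation by arm is barred, or that complications are never compared by dose. Step 1 refutes the first. The text neither requires nor forbids evaluation by coded arm after a pause. Section 2 makes complications secondary outcomes of a four-group comparison. The gap is during enrollment only.

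The check schedule also matters. If the 20% rule were applied after every woman from the tenth onward, a pooled rate of 12.5% would trigger a pause in about 36% of trials, not about 20%. The misses would then be fewer, but the signal would be no more specific to dose.

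Finally, repeated unadjusted Fisher tests are a debatable choice. That is accepted, and the flag is left optional.

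**Conclusion.** The point holds in this limited form. The pause tracks the pooled event rate, and nothing described during enrollment would show whether events cluster on high dose. That structural conclusion needs no assumed rates. Its size does: identical 76% pause rates for 10% vs 30% and for 20% in both arms; then either 95% pauses with no dose effect (nausea/vomiting counted, adding 20% to a 5% background) or 81% missed at 5% vs 20% (not captured, low background). These figures rest on assumed rates, balanced blocks and checks every 10 women. The matter is worth correcting for safety monitoring and does not affect the efficacy analysis.

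**What to change.** Make these changes together:

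1. Keep the 20% pooled pause, but leave nausea and vomiting out of its count, and say which events do count.
2. Tabulate AEs and SAEs separately.
3. At each 10-enrollment review, and in the evaluation after any pause, give the already-planned independent reviewer these counts by coded arm (A/B), with the principal investigator and care team kept blinded.
4. Optionally, add a between-arm flag that prompts evaluation by dose, with a threshold agreed by the trial's clinicians. Step 3 shows what one example would give.

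Keep individual handling of SAEs, since no count rule at this size detects rare ones. The changes do not remove pauses when counted events are common in both arms; they let the reviewer see that the events are shared.

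The cost is protocol wording and a short table every 10 women. The pharmacy holds allocation but section 12 keeps the study data on the principal investigator's computer, so the two must be linked. One route is to send events by study number to the pharmacy, which returns the coded table directly to the reviewer. A departmental reviewer assigned by the principal investigator would then see coded-arm counts. Dropping nausea and vomiting makes the pooled pause quieter, which is why it should not be done without the coded-arm table.

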A data collection sheet will be used to record data. This data will then be stored in a coded fashion with key code assigned, in a computer excel spreadsheet on the principal investigator's computer, located in room 8327G in the Department of Obstetrics and Gynecology. Only the PI will have access to the key code. Because every account on the computer is password protected, the only person who has access to this computer is the PI herself. Only personnel on the VOTF will be granted access to this data/spreadsheet. The data collection sheet and the patient consent forms will be kept in the same room in a locked file cabinet. These data collection sheets, the patient consent documents as well as the key code will be stored for a period of 6 years after conclusion of study and destroyed thereafter.

13) Access to Private Information

a. Access to medical records (HIPAA): Patients agreeing to participate in this study will be made aware that record review of their, and their child's, protected health information will occur as a part of the study. The consent form includes HIPAA consent. Only investigators on the VOTF can access their PHI, as described above. A list of data to be collected is detailed above.

14) Subject compensation

There will be no monetary compensation provided to the subjects for participating in this study.

15) Medical care and compensation for injury

There are no expected maternal or fetal injuries attributed to the high dose oxytocin regimen compared to the low dose oxytocin regimen as discussed above. In the unforeseeable event that a complication occurs, the patient will be billed for their medical care as they would with any other induction of labor.

16) Monitoring for subject safety

The study protocol has built in monitoring measures for specific clinical scenarios in the setting of adverse reactions. These include specific detailed protocols for tachysystole, nonreassuring fetal status as well as oliguria.

For every 10 enrollments, data will be monitored by the principal investigator and reviewed by an independent reviewer within the department of ob/gyn. This personnel will have a background in ob/gyn and will be assigned by the principal investigator. Data will be reviewed in a blinded fashion to prevent introducing bias into the study. In addition, all serious adverse events (SAE) will be monitored and documented closely during the study with each enrollment, and will result in discontinuation of the study protocol immediately. The management of AE is detailed in the protocol. If more than 20% of patient enrolled in the study have an AE/SAE, enrollment in the study will be stopped pending an evaluation of the frequency of AE/SAE. This will be reported to the IRB. The principal investigator and the research staffs will monitor protocol adherence closely with each enrolled participant. Any protocol deviation will be reported to the IRB as required.

17) Withdrawal of subjects

A patient may withdraw from this research at any time. The infusion of the study drug can be stopped at any time. A patient may withdraw for any reason, including a desire to stop induction of labor and undergo an elective cesarean delivery. Subjects will not be at increased risk when they are abruptly withdrawn from the study because of the short half-life of oxytocin (4.5 minutes). Data collection on patients who have completed more than 30 minutes of study drug will be kept and included in the data analysis (intention to treat analysis). Any withdrawal secondary to side effects or adverse effects will be recorded and monitored. Only verbal withdrawal is required.

18) Sharing of results with subjects

The results of the study will not be shared with the subjects, families or the institution. Patients will not be contacted in the future in relation to the results of the research. The intention is to publish the results of this research and patients will have access to the information gained through this forum.

There will be no additional charges billed to the insurance for any procedures associated with this study.

19) Future use and long-term storage of data or specimens

Data will not be kept for future research.

20) Clinical Trials.gov Information

	ClinicalTrials.gov "NCT" number for this trial (provide):
\boxtimes	Registration pending
	Clinical trial does not require registration (explain):

SECTION 4: LIST OF ATTACHMENTS FOR THIS SUBMISSION (REQUIRED) (Items listed here are expected to be attached as separate documents. These documents will appear in the UA HSPP IRB approval letter as 'documents submitted concurrently' with the review.)

Document Name	Version Date
1. F107/VOTF	1. 02/27/17
2. Appendix A/Children	2. 02/27/17
3. Appendix B/Drugs/devices	3. 02/27/17
4. Appendix D/pregnant women and neonate	4. 01/31/17

5. Drug information	5. 01/31/17
6. Appendix F/waiver of consent	6. 02/27/17
7. T503a/consents	7. 03/31/17
8. Data collection form	8. 01/31/17
9. Biosketch of PI ([name]) and Co PI ([name])	9. 02/27/17
10. Protocol	10. 03/31/17
11. autographs	11. 01/31/17

See HSPP website for submission requirements.

Items needed for approval:

- Word Versions of Application, Consents, Recruitment and Data Collection
- F107: Verification of Training Form
- Current PI/Co-PI CVs or biosketch, if not included with copy of grant application
- Informed Consent/Permission/Assent Form(s) including study specific release of information documents, DHHS
 approved sample consent forms. If consent will not be documented in writing, a script of information to be provided
 orally to subjects

Other Items as applicable:

- Appendix A Children
- Appendix B Drug/Device
- Appendix C- Multi Site Research
- Appendix D- Pregnant Women and Neonates
- Appendix E- Prisoners
- Appendix F- Waiver of Consent/ PHI
- Appendix G- Exception from Informed Consent (EFIC)
- Appendix H- Native American
- Biosafety Review letter (for UA Institutional Biosafety Committee)
- Certificate of Confidentiality
- Compressed Gases Review letter (for UA Research Instrumentation)
- Contract complete or draft copy of contract including budget
- Data Collection Tools surveys, questionnaires, diaries not included in the protocol, data abstraction form for records review
- Data Monitoring Charter and Plan
- Drug/Device information Investigator's Brochure, drug product sheet, device manual, user's manual, instructions
 for use, package insert, IND/IDE documentation, FDA 1572 form, 510k indication, FDA exemption, sponsor
 determination of device risk, etc.
- Export Control Review
- **Grant Application(s)** cover-to-cover copy of grant, regardless of home institution or funding agency, and a copy of the Notice of Grant Award.
- Multi-site information (for sites engaged in research where the UA is the IRB of record)
 - Copy of any approvals granted from that site (including determinations if this site has an IRB of its own)
 - Site-specific F107
 - Copy of the site's human subjects training policy
 - CV and medical license (if applicable) of site PI
- Other Approval letters (e.g., school districts, Tribal, other IRB approvals)
- Participant Materials written materials to be provided to or meant to be seen or heard by subjects (e.g. study newsletter, physician to participant letter, wallet cards, incentive items, holiday/birthday cards, certificates, instructional videos/written guides, calendars, certification of achievement, etc.)
- Payer coverage analysis

- PHI Authorization Form(s)
- **Protocol** including all amendments/revisions, sub- or extension-studies
- · Radiation Safety Review letter- needed regardless if the radiation device is approved and used standard of care
- **Recruitment Materials** telephone scripts, flyers, brochures, websites, email texts, radio/television spots, newspaper advertisements, press releases, etc.
- **Scientific Review Committee** letter (for cancer related projects AZCC SRC; other units as applicable if the unit has a scientific review committee)
- Site Authorizations for research purposes and/or access to administrative records/samples
 - External sites (such as schools, other hospitals or campuses, etc.)
 - UAHS Research Portal feasibility review approval
- Travel Authorization documentation (for UA Office of Global Initiatives)
- Use of retrospective research samples and/or data IRB approval letter, original consent under which samples/data were collected, letter allowing access to samples
